7.1.1. Sensitivity Analyses

The first sensitivity analysis will be conducted to evaluate the robustness of the primary model using normality of log-transformed 24-hour UPCR data assumption. A stratified rank ANCOVA analysis [LaVange and Koch 2006] will be conducted without using the normality assumption of log-transformed 24-hour UPCR data. The following steps will be performed:

- 1. Standardized ranks within each stratification stratum will be derived across the two treatment groups for the baseline and the change from baseline at Week 32 in 24-hour UPCR
- 2. The linear regression model will be fitted separately for each stratum where the standardized rank of the change from baseline at Week 32 in 24-hour UPCR is the outcome variable, the standardized rank of the baseline is the only covariate
- 3. The stratified mean score test will be performed to compare the two treatment groups using the values of the residuals from the above model as scores and stratification factor as the stratum
- 4. Cochran-Mantel-Haenszel (CMH) p-value is obtained

The second sensitivity analysis is to assess the impact of missing data and the robustness of the primary analysis. The analysis will use the same MMRM model on the imputed data, of which the missing 24-hour UPCR value will be imputed with the spot UPCR [Ginsberg 1983; Viswanathan and Upadhyay 2011] assessed closest to the date of missing value, when available. Depending on the extent of missing values this sensitivity analysis might not be needed.

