• Modified Intent-to-Treat Analysis Set (mITT): All patients who receive any amount of study drug and have baseline and at least one post-baseline 24-hour urine protein creatinine ratio assessment. Patients will be grouped by assigned treatments (i.e., as randomized).

- Safety Analysis Set: All patients who receive any amount of study drug. Patients will be analyzed according to the treatment actually received.
- PK Analysis Set: All patients who receive a full dose of study drug and have at least 1 PK concentration measurement.
- PD Analysis Set: All patients who receive a full dose of study drug and who have at least one post-dose blood sample for the determination of plasma C5 level.
- All Cemdisiran Treated Set: All patients who receive at least one dose of cemdisiran, including patients who take cemdisiran during the DB period and patients who first take placebo during the DB period and switch to cemdisiran during the OLE period.

The primary population used to evaluate efficacy will be the mITT Population unless stated otherwise. Safety will be analyzed using the Safety Analysis Set. The PK and PD Analysis Sets will be used to conduct PK and PD analyses, respectively. The All Cemdisiran Treated Set will be used to summarize long-term efficacy and safety of cemdisiran.

4.2. **Protocol Deviations**

Protocol deviations will be classified into major or minor deviations by medical review. A major deviation is defined as a deviation that may significantly impact the completeness, accuracy and/or reliability of the trial data; that may significantly affect a patient's rights, safety and wellbeing (ICH.E3 R1 Structure and Contents of Clinical Study Reports Guidance for Industry. 2013). Major protocol deviations will be reviewed and approved by Alnylam prior to the interim database lock for the primary analysis of the DB treatment period. All protocol deviations will be presented in a listing. The Sponsor or designee will be responsible for producing the final protocol deviations file. This file will include at a minimum each protocol deviation and whether or not this deviation is classified as a major protocol deviations. This file will be finalized prior to the primary treatment phase database lock. Protocol deviations will be summarized in the CSR.

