5.3. Baseline Definitions

Baseline value for 24-hour UP, UPCR, and UACR will be calculated as the average of two valid (as per section 6.4.1.1 of the protocol) collections at week -2 visit (i.e., the last measurement prior to the first dose of study drug). Baseline values for vital signs will be defined as the assessments at week -2 visit because of the required vaccination when applicable. The baseline value for an ECG variable (heart rate, PR interval, QRS interval, QT interval or QT_c interval) will be the average of last triple assessments prior to the first dose of study drug (Day 1). For other parameters, baseline is defined as the last non-missing value prior to the first dose date/time of the study drug, unless otherwise specified.

For the All Cemdisiran Treated Set, baseline for patients randomized to cemdisiran in DB period is as defined above. For patients who switched from placebo in the DB period and received at least one dose of cemdisiran in the OLE period, baseline for all parameters will be redefined as the last non-missing assessments prior to the first dose of cemdisiran, except for assessments based on 24-hour urine collections where the average of the two valid collections at week 32 visit will be the baseline value and for ECG variables where the average of the last triplet assessments prior to the first dose of study drug in OLE period will be the baseline.

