7. STATISTICAL ANALYSIS

7.1. Primary Endpoint

The primary endpoint of the study is the percent change from baseline in urine protein/creatinine ratio [UPCR] as measured in 24-hour urine at Week 32. The analysis will be conducted using the modified ITT analysis set.

Valid 24-hour urine protein values collected during the DB period will be included in the primary analysis (1 valid assessment at week 16 visit and the mean of two valid assessments at baseline and week 32 visit). All 24-hour urine samples need to meet the validity criteria below (Section 6.4.1.1 of the protocol). The 24-hour UPCR at baseline or Week 32 is the average of two valid collections.

A 24-hour urine collection will be considered valid if the following criteria are met:

- The collection is between 22-26 hours in duration between the initial discarded void and the last void or attempt to void.
- No voids are missed between the start and end time of the collection as indicated by the patient's urine collection diary.

The resulting 24-hour UPCR at each visit will be log transformed for analyses.[Fellstrom 2017; Li 2006] The primary analysis will be performed using a restricted maximum likelihood (REML) based Mixed-Effect Model Repeated Measures (MMRM) approach. The outcome variable is change from baseline in 24-hour UPCR in log-scale at week 16 and week 32 visits. Analysis will include fixed effects of treatment (cemdisiran vs. placebo), scheduled visits (week 16 and week 32), interaction term of treatment and scheduled visits, baseline 24-hour UPCR in log-scale (continuous), and patient as a random effect. Unstructured working correlation will be used to model the within-patient errors. If the fit of covariance structure fails to converge, independent correlation structure will be used. At each visit, least square (LS) means ($\hat{\mu}_j$) with corresponding standard errors (SEM) and 90% CI will be displayed by treatment arm. The primary comparison is the LS mean treatment difference (cemdisiran – placebo) in percent change of 24-hour UPCR at week 32 visit from baseline. This LS mean difference will be presented along with corresponding standard errors (SEMs), 90% CIs and p-value from the model.

The following results will also be presented:

• Placebo-adjusted geometric mean percent change at week 32 visit:

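### The missing-data sensitivity analysis subtracts a 24-hour baseline from a raw spot UPCR, so any offset between the two specimens enters the imputed patients' change

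*SAP*

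**What the plan says.** Section 7.1.1 plans two sensitivity analyses. The stratified rank ANCOVA drops the normality assumption. Only the second concerns missing data: "the missing 24-hour UPCR value will be imputed with the spot UPCR", choosing the spot value "assessed closest to the date of missing value, when available". Two literature references are cited for using spot samples. No agreement figure, calibration or maximum time distance is given. Then "The analysis will use the same MMRM model on the imputed data". The section ends: "Depending on the extent of missing values this sensitivity analysis might not be needed".

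The model being reused is in section 7.1: "The outcome variable is change from baseline in 24-hour UPCR in log-scale at week 16 and week 32 visits", with the log 24-hour baseline as covariate. Section 5.3 defines that baseline: "Baseline value for 24-hour UP, UPCR, and UACR will be calculated as the average of two valid" collections at Week -2. Section 4.1 admits to the mITT set only patients who "have baseline and at least one post-baseline 24-hour urine protein creatinine ratio assessment", so a 24-hour baseline is always present. Section 7.2 (Table 2) uses a baseline spot UPCR in the separate spot UPCR analysis, so that measurement is also collected.

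**The concern.** A change score is meant to compare like with like. Here the follow-up value can come from one kind of specimen and the baseline from another. If spot UPCR reads systematically lower or higher than 24-hour UPCR, the gap does not cancel, and the model cannot distinguish it from a real fall or rise in proteinuria.

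A single spot reading also enters as if it were the measured 24-hour value, at Week 32 in place of a two-collection mean. The standard error therefore takes no account of the value having been imputed.

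Finally, whether to run the analysis is left to judgement with no threshold. Section 2.3 says that sponsor personnel are not blinded, so the rule is better fixed in advance. At stake is whether the plan's one check on missing data gives a clean answer or adds an artefact of its own.

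**Working it through.** **1. The plan's own figure.** Section 5.1 gives log SD 0.597, 9 placebo and 18 cemdisiran patients, and geometric mean ratios (GMRs) of 0.88 and 0.50.
- SE = 0.597 × √(1/9 + 1/18) = 0.2437.
- 90% half-width = 1.645 × 0.2437 = 0.401, so the width is 0.802. The stated 0.80 (±0.4) is reproduced.
- Planned effect = ln(0.50/0.88) = -0.565, a placebo-adjusted change of -43.2%.

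**2. What an imputed change contains.** Let r be the ratio of spot to 24-hour UPCR at the visit. Then

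ln(spot) − ln(24-hour baseline) = [ln(24-hour at visit) − ln(24-hour baseline)] + ln(r).

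The bracket is the wanted quantity and ln(r) is the artefact. With r = 0.80, a patient whose proteinuria has not changed is scored as a 20% reduction.

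**3. From patient to arm to difference.** With m of n values imputed in an arm and a common r:
- shift in arm mean = ln(r) × m/n
- shift in treatment difference = ln(r) × (m_c/n_c − m_p/n_p), where c is cemdisiran and p is placebo

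The second expression is zero when the imputed shares are equal. It is non-zero if the shares differ, and in general also if r itself differs by arm.

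**4. Size when only placebo values are imputed.** The SAP states neither r nor the number missing. Assume 2 of 10 placebo and 0 of 20 cemdisiran values are imputed. The placebo mean then shifts by 0.2 × ln(r), and the difference shifts by the same amount with the opposite sign.

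| Assumed r | ln(r), per imputed patient | Shift in difference | Placebo GMR (0.88 planned) | Placebo-adjusted change (-43.2% planned) |
|---|---|---|---|---|
| 0.90 | -0.105 | +0.021 | 0.862 | -42.0% |
| 0.80 | -0.223 | +0.045 | 0.842 | -40.6% |
| 0.70 | -0.357 | +0.071 | 0.819 | -39.0% |

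Against the 0.40 half-width, the shift runs from 0.02/0.40 = 5% to 0.07/0.40 = 18%.

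**5. Other splits, using the 18 and 9 patients of section 5.1.**
- r = 0.80, imputed 4/18 and 2/9: the arm GMRs move from 0.500 and 0.880 to 0.476 and 0.837. The placebo-adjusted change stays at -43.2%.
- r = 0.80, imputed 1/18 and 3/9: shift +0.062, giving -39.5%.
- r = 0.80, imputed 4/18 and 0/9: shift -0.050, giving -45.9%.
- r = 1.25, same two unequal splits: shifts -0.062 and +0.050, giving -46.6% and -40.3%.

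The direction therefore depends on both the sign of the offset and the arm with more imputed values.

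**6. Check by simulation.** A Week 32 ANCOVA with baseline as covariate stood in for the MMRM (4,000 runs, assumed spot noise SD 0.3). With r = 0.80 it gave -0.498 for the 1/18 and 3/9 split (formula: -0.565 + 0.062 = -0.503) and -0.614 for 4/18 and 0/9 (formula: -0.565 − 0.050 = -0.615). The agreement is within simulation error.

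**7. After calibration.** If spot is related to 24-hour UPCR before use, a constant ln(r) is absorbed. The offset then shifts neither the arm means nor the difference.

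**The case against.** The strongest reply is that the effect on the primary comparison is small and rests on assumptions. No offset is documented, and the SAP cites sources for the substitution that cannot be consulted here. Even the 30% case with one-sided imputation moves the difference by less than a fifth of the planned half-width, in a Phase 2 study whose comparisons section 5.5 calls descriptive. All of this stands. A reader might infer that the treatment difference is always biased, or that the analysis could create or conceal a discrepancy on its own. The documents do not support either: equal shares with a common offset leave the difference unchanged. The per-patient shifts should also be judged against the patient-level SD of 0.597, not the between-arm effect of -0.565.

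Second, section 7.2 already plans a spot-to-spot MMRM in which a constant offset cancels. That is useful context, but it is a different endpoint and does not repair the missing 24-hour values.

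Third, using spot minus baseline spot would bring in the noise of a second spot specimen, and would be worse if the true offset were near zero. This is a fair objection to that remedy, but not to multiple imputation or calibration.

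Two further readings go too far:
- With no limit on distance in time, a placebo patient's nearest spot could fall after the first open-label cemdisiran dose. That needs the nearer double-blind spots to be missing too. Section 7.1 confines the 24-hour values to the double-blind period, and the spot schedule is in the protocol, which is not shown. It is an edge case worth excluding in a phrase.
- A patient with one valid Week 32 collection might be thought to lose it to a spot value, because "The 24-hour UPCR at baseline or Week 32 is the average of two valid collections". That question concerns the endpoint definition in section 7.1, which refers to the protocol for collection validity. It is not a fault of the imputation rule.

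The option to skip is tied to the extent of missing data, and with nothing missing the analysis would simply repeat the primary one. The remaining criticism is that no threshold is stated.

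**Conclusion.** The point holds as an inexpensive improvement to the plan. As written, the only missing-data sensitivity analysis mixes specimen types within one change score, so any systematic spot-to-24-hour difference enters the imputed patients' change and the reported arm-level GMRs. The treatment difference is affected only if the imputed share or the offset differs by arm. It then moves by about 0.02 to 0.07 log units under the assumed 10% to 30% offset with 2 of 10 placebo and no cemdisiran values imputed. Treating the spot value as observed also leaves out imputation uncertainty, whatever the offset. The primary analysis is not affected, and nothing here shows that its conclusion would change.

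**What to change.** In section 7.1.1, replace direct substitution with multiple imputation of the missing log 24-hour UPCR, using the 24-hour baseline, the baseline spot and the visit spot UPCR as predictors, together with treatment arm. Fit the primary MMRM to each completed data set and pool the results so that the interval reflects the imputation. A simpler alternative is to calibrate log spot to log 24-hour UPCR on visits where both were measured and impute the calibrated value; calibration alone removes the offset but still treats the imputed value as known.

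Restrict eligible spot values to the double-blind period before the first open-label dose, and state a maximum distance in time. Delete the sentence that makes the analysis optional, and run it whenever any Week 32 24-hour UPCR is missing.

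The cost is an SAP wording change, a little more programming and slightly wider intervals. With about 30 patients the imputation model must stay small, and the plan should say what is done for a patient who lacks a baseline or visit spot value.

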7.1.2. Subgroup Analyses

Subgroup analyses will be conducted to assess the treatment effect during the DB period for the primary endpoint within the following subgroups: race (Asian vs. non-Asian), gender (Male vs. Female), age (< Median vs. \geq Median), baseline eGFR (< 60 ml/min/1.73m² vs. \geq 60 ml/min/1.73m²), and baseline 24-hour UP (>=1g/24-hour and < 2g/24-hour vs. \geq 2g/24-hour). Other subgroups may be examined, if deemed appropriate.

The subgroup analysis will be performed for the primary endpoint using the mITT analysis set. A forest plot will be generated to illustrate the estimated treatment effect along with the associated 90% confidence interval. The subgroup analyses may be performed for secondary endpoints if appropriate.

7.2. Secondary Endpoints

For secondary endpoints assessed in DB period, the analysis will compare randomized arms (cemdisiran vs. placebo) using the mITT analysis set.

The secondary endpoints which are assessed beyond Week 36 will be summarized to describe the long-term efficacy of cemdisiran using the All Cemdisiran Treated Analysis Set by treatment sequence, i.e., cemdisiran/cemdisiran, placebo/cemdisiran, and All Cemdisiran.

The planned analyses of the secondary endpoints are summarized in Table 2.

Endpoint	Statistical Method	Notes
Percent of patients with partial clinical remission (urine protein [UP] <1.0g/24-hour) at Week 32	Treatment comparison will be conducted using Cochran-Mantel- Haenszel test stratified by baseline 24- hour UP (≥ 1g/24-hour and <2 g/24-hour	
Percent of patients with >50% reduction in 24-hour proteinuria at Week 32	vs. ≥ 2 g/24-hour). The number and percentage of patients who are responders at Week 32 are summarized by treatment arm.	
	The difference in percentages of responders and corresponding 90% CI based on the Wilson score method with continuity correction will be presented.	

 Table 2
 Summary of Analyses for the Secondary Efficacy Endpoints

Endpoint	Statistical Method	Notes
Percent change from baseline in 24-hour proteinuria (g/24- hour) at Week 32	Treatment comparison and estimates will be conducted by a similar MMRM model used for the analysis of primary endpoint. Descriptive statistics will also be generated by treatment arm at each scheduled visit. Geometric Mean (with 90% CI) figures of the ratio to baseline by treatment arm will be plotted as well as individual spaghetti plots.	
Change from baseline in UPCR as measured in a spot urine at Week 32	The change from baseline in log- transformed spot UPCR by visit through Week 36 will be analyzed via a MMRM model. The model includes log- transformed baseline spot UPCR, treatment, visit, and the interaction of treatment and visit. Robust errors [White 1980] will be used to model the within-patient errors. Descriptive statistics will also be generated by treatment arm at each scheduled visit. Geometric Mean (with 90% CI) figures of the ratio to baseline by treatment arm will be plotted as well as individual spaghetti plots.	Scheduled assessments are outlined in the Table 1 (Schedule of Assessments) of the protocol.
Change from baseline in hematuria at Week 32	Shift tables for both assessment methods (microscopic examination and urine dipstick) will be presented	Results using microscopy and dipstick are both in range categories.

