2. STUDY OVERVIEW

2.1. Study Design

This study is a multicenter, double-blind, placebo-controlled study comprised of three periods (Figure 1). Eligible patients will begin a 14-week observational run-in period during which treatment with the standard of care is expected to remain unchanged. At the end of run-in period, patients whose average urine protein (UP) of two valid urine collections is at or higher than 1g/24-h are eligible for randomization into the 36-week double blind (DB) period. Approximately 30 patients are planned to be randomized in a 2:1 ratio, 20 in the cemdisiran arm and 10 in the placebo arm in the DB period, which is followed by a 156-week open-label extension (OLE) period to further evaluate the long-term safety and efficacy. All patients will be followed for safety for 52 weeks after the end of study visit.

The independent Data Monitoring Committee (DMC) will have access to subject level treatment assignments and perform periodic reviews of unblinded data throughout. Details are provided in the DMC Charter of the study.

Figure 1 Study Design

days)	Run-in Period (14 Weeks)		Treatment 1 (36 Wee	Freatment Period (36 Weeks)		sment	Open-label Extension (156 Weeks)		iod	
Screening (up to 120 c	Standard of care	mization (2:1	ALN-CC5 600mg Q4W (n=20) + Standard of care)T k 32)	S ¢ 36)	ndpoint asses	ALN-CC5	DT (c 184) 0S (s 188)	SS (188)	ty Follow-up (2 Weeks)
		Rando	Placebo (n=10) + Standard of care	EC (Wee	EC (Wee	Primary e	+ Standard of care	EC (Week	EC (Week	Safe (5

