5. GENERAL STATISTICAL METHODS

5.1. Sample Size Justification

The sample size of the study was determined based on the precision of the estimate of the treatment effect for the primary endpoint – the percent change from baseline in urine protein/creatinine ratio [UPCR(mg/mg)] as measured in 24-hour urine at Week 32. It should be noted that geometric mean ratio of UPCR at Week 32 to baseline is statistically equivalent to mean of the change from baseline in logarithm of UPCR. Therefore, the effect size of the study is defined as the difference of change from baseline between cemdisiran and placebo in the logarithm of UPCR.

Based on the NEFIGAN study, [Fellstrom 2017] we assume that in the placebo arm the geometric mean ratio of UPCR at Week 32 to baseline is 0.88 (log standard deviation [SD] 0.597), corresponding to a 12% reduction, while the geometric mean ratio is 0.5, or a 50% reduction for the cemdisiran arm. Using these assumptions, sample size of 9 and 18 in the placebo and cemdisiran arms will provide a width of 0.80 (+/- 0.4) for the 90% confidence interval (CI) for treatment effect size estimate (cemdisiran – placebo) in log scale.

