5.7. Visit Windows

For table and figure summaries of the DB period, all data will be tabulated and analyzed per the evaluation visit as recorded on the electronic case report forms (eCRF) even if the assessment is outside of window.

For table and figure summaries during cemdisiran treatment period, the data collected at study visits during the OLE period will be re-mapped for the patients randomized to placebo in the DB period to reflect the visit relative to the first dose of cemdisiran. Unless otherwise specified, data collected at an unscheduled visit will be included in by patient listings and/or spaghetti plot figures, but no assignment of the scheduled visit will be made for the purposes of summary tabulations. However, unscheduled study visits will be used in categorical shift tables (e.g. shift from baseline to worst post-baseline value).

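### Long-term partial-remission summaries count placebo crossovers already below 1.0 g/24 h before their first cemdisiran dose, and do not set them apart

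*SAP*

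**What the plan says.** The relevant provisions are spread over several sections of the current SAP.

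- **Endpoint (Section 7.2, Table 2).** The endpoint is "Percent of patients with partial clinical remission (urine protein [UP] <1.0g/24-hour) at Week 32". It is an absolute threshold with no baseline term.
- **Long-term use (Section 7.2).** "The secondary endpoints which are assessed beyond Week 36 will be summarized to describe the long-term efficacy of cemdisiran". These tables are built on everyone who ever received the drug, with one column per treatment sequence and a pooled column.
- **Who is in that set (Section 4.1).** It includes "patients who first take placebo during the DB period and switch to cemdisiran during the OLE period". No proteinuria level is required of them.
- **Their baseline (Section 5.3).** For measures from 24-hour urine, the baseline is reset to the point "where the average of the two valid collections at week 32 visit will be the baseline value". Those collections are made while the patient is still on placebo.
- **Their visits (Section 5.7).** Extension visits are "re-mapped for the patients randomized to placebo in the DB period to reflect the visit relative to the first dose of cemdisiran".
- **Entry level (Section 2.1).** At the end of the run-in, "patients whose average urine protein (UP) of two valid urine collections is at or higher than 1g/24-h are eligible for randomization". The SAP states this threshold for randomisation only.

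**The concern.** A fixed threshold shows that a patient improved only if the patient started on the other side of it. In the double-blind period everyone does, because entry requires at least 1 g/24 h. Patients randomised to cemdisiran keep that baseline in the long-term tables. Crossovers do not: their clock restarts at Week 32, and by then some may have fallen below 1.0 g/24 h on placebo. If such a patient is still below at an extension visit, the placebo/cemdisiran and All Cemdisiran columns count a remission that was reached before any cemdisiran was given.

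The stated purpose of these tables is to describe cemdisiran's long-term efficacy, and only about 10 patients can cross over. Each patient carried in this way therefore moves the crossover percentage visibly, and a reader of the table cannot tell a remission reached on cemdisiran from one reached on placebo.

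**Working it through.** **1. The SAP's own figure.** Section 5.1 assumes that "in the placebo arm the geometric mean ratio of UPCR at Week 32 to baseline is 0.88 (log standard deviation [SD] 0.597"), and states a 90% CI width of 0.80 with 9 and 18 patients. Half-width = 1.645 × 0.597 × √(1/9 + 1/18) = 0.401, so the width is 0.802. The figure reproduces with the normal quantile (0.833 with t on 25 df). The point here does not depend on it, but it confirms how the 0.597 is used: as the SD of the log ratio to baseline.

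**2. Starting levels, side by side.**

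| | Cemdisiran/cemdisiran | Placebo/cemdisiran |
|---|---|---|
| Cemdisiran baseline for 24-hour urine | Week -2, mean of two valid collections (5.3) | Week 32 on placebo, mean of two valid collections (5.3) |
| Minimum UP at that baseline | 1 g/24 h (2.1; strata in 5.4) | none stated |
| Can meet the remission definition before first cemdisiran dose | no | yes |

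The SAP has no rule that excludes, flags or separately counts the patients in the last cell. Its UP categories (1 to under 2 g, and 2 g or more) have no level for them.

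**3. How many might there be?** The inputs are ratio 0.88 and log SD 0.597 (Section 5.1) and 10 placebo patients (Section 2.1). The assumptions are:
- the UPCR figures carry over to 24-hour UP;
- the change does not depend on the entry level;
- all 10 placebo patients cross over.

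The SAP gives no distribution of entry UP, so a range is shown. For entry UP = U,

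P(Week 32 UP < 1.0) = Φ[(−ln U − ln 0.88) / 0.597].

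Example, U = 2.0: (−0.693 + 0.128)/0.597 = −0.947, and Φ = 0.172.

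| Entry UP (g/24 h) | P(below 1.0 at Week 32 on placebo) | Expected of 10 |
|---|---|---|
| 1.25 | 43.7% | 4.4 |
| 1.5 | 32.1% | 3.2 |
| 2.0 | 17.2% | 1.7 |
| 2.5 | 9.3% | 0.9 |
| 3.0 | 5.2% | 0.5 |
| 4.0 | 1.8% | 0.2 |

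The same formula, averaged by simulation over lognormal entry values truncated at 1 g or more:

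| Median before truncation, log SD | Median after truncation | P | Expected of 10 | P(at least one) = 1 − (1 − P)^10 |
|---|---|---|---|---|
| 1.5, 0.4 | 1.62 | 28.4% | 2.8 | 96.5% |
| 2.0, 0.5 | 2.11 | 19.0% | 1.9 | 87.9% |
| 2.5, 0.5 | 2.55 | 13.7% | 1.4 | 77.1% |

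**4. Weight in the tables.** A carried-in patient who is still below 1.0 g at the visit adds 1/10 = 10 points to placebo/cemdisiran and 1/30 = 3.3 points to All Cemdisiran. Two add 20 and 6.7 points; three add 30 and 10.

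**5. Illustration of the split, with invented counts.** Suppose 2 of 10 crossovers are carried in and stay below, 3 of the other 8 reach remission, and 10 of 20 cemdisiran/cemdisiran patients are in remission. As planned, placebo/cemdisiran shows 5/10 = 50% and All Cemdisiran 15/30 = 50%. Among patients at or above 1.0 g at their cemdisiran baseline, the figures are 3/8 = 37.5% and 13/28 = 46.4%.

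**The case against.** The other side has a good deal to say, and part of it limits the point.

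- **A reader might infer that a drug with no effect would show 14% to 28% remission after crossover.** The documents do not support this. Those percentages are the chance of being below 1.0 g at re-baseline. The rate at later visits depends on how many patients drift back above or newly fall below, and the SAP gives nothing from which to model that.
- **A reader might infer that the crossover column is inflated by that amount relative to cemdisiran/cemdisiran.** This is not supported either. Both arms enter from the same population, so a drug adding nothing to placebo would give the cemdisiran/cemdisiran column the same background rate at Week 32. The columns differ in starting state; the calculation does not estimate an excess.
- **The reset baseline changes nobody's remission status**, because the endpoint has no baseline term. This is correct. The problem is that crossovers enter a cemdisiran efficacy table with no condition on, or display of, their status before the drug.
- **Much of the information appears elsewhere.** Table 2 gives Week 32 responders by arm, individual UP plots are planned, and Section 5.10 plans a within-patient comparison of 24-hour UP. The endpoint of more than 50% reduction is relative, so it does not reward starting low. All this softens the problem, but none of it changes how remission on cemdisiran is counted. The within-patient comparison does not list remission.
- **Table 2 names the endpoint at Week 32.** Its long-term use rests on the separate sentence about endpoints assessed beyond Week 36, which makes no exception for remission, and on the visit re-mapping. That reading is reasonable, though it is an inference.
- **The summaries are descriptive (Section 5.5), and the protocol, which is not at hand, may restrict entry to the extension.** If it does, the added row would simply be empty.

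**Conclusion.** The point holds as a matter of reporting. For partial remission in the All Cemdisiran Treated Set, the SAP counts crossovers already below 1.0 g/24 h at their Week 32 re-baseline as in remission on cemdisiran if they are still below at the extension visit, and it does not separate them. Patients randomised to cemdisiran cannot start in that state.

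For assumed median entry UP of about 1.6 to 2.6 g/24 h, roughly 1 to 3 of 10 placebo patients would be affected; if entry UP is 3 g or more, fewer than 1. The size rests on the assumptions listed in the working, above all on an entry distribution that the SAP does not give. It is not an estimate of the extension-period rate under no drug effect. The double-blind comparison and the cemdisiran/cemdisiran rate are untouched. This is a cheap improvement to a descriptive table and does not threaten the trial's main result.

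**What to change.** In Section 7.2, for All Cemdisiran Treated Set summaries of partial remission, keep the overall percentage and add rows by status at the patient's own cemdisiran baseline:

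- remission among patients at or above 1.0 g/24 h at that baseline;
- maintained or lost remission among patients already below 1.0 g/24 h at that baseline, shown as counts because the group will be very small.

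State that any claim about remission achieved on cemdisiran rests on the patients at or above 1.0 g. Full remission (under 0.3 g/24 h) is an exploratory endpoint in Section 7.3, where extension beyond the double-blind period is optional. Apply the same split, at its own threshold, only if it is summarised there.

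The split does not bring the rate under no drug effect to zero. Patients who start just above 1.0 g can still fall below it by ordinary variation (43.7% over 32 weeks on placebo from 1.25 g, by the formula in the working). It removes only the remissions that predate the drug.

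The cost is a sentence of SAP text, one extra table row, and a placebo/cemdisiran denominator smaller by about 1 to 3 patients in the row that carries the claim. No new data are needed, and the double-blind analysis stays as it is.
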